5.1. Inclusion Criteria

Participants are eligible to be included in the study only if all of the following criteria apply:

- 1. Ability to comprehend and willingness to sign a written ICF for the study.
- 2. Age \geq 18 years at the screening visit.
- 3. Diagnosis of CHE for at least 6 months prior to screening.
 - Diagnosis of CHE is defined as HE lasting > 3 months or ≥ 2 recurrences within the previous 12 months.
 - *Note:* Participants with hyperkeratotic, vesicular (eg, pompholyx), and fingertip eczema may be included.
- 4. Screening and baseline IGA-CHE score of 3 or 4.
- 5. Baseline CHE-related Itch NRS score ≥ 4. Baseline Itch NRS score is defined as the 7-day average of Itch NRS score directly before Day 1 (data from a minimum of 4 out of 7 days prior to Day 1 is needed).
- 6. Have been treated with at least 1 prescription CHE therapy or if such therapy was not advisable or contraindicated.
- 7. Willingness to avoid pregnancy or fathering children based on the criteria below.
 - a. Male participants with reproductive potential must agree to take appropriate precautions to avoid fathering children from screening through 90 days (a spermatogenesis cycle) after the last application of ruxolitinib cream and must refrain from donating sperm during this period. Permitted methods in preventing pregnancy (see Appendix A) should be communicated to the participants and their understanding confirmed.
 - b. Female participants who are WOCBP must have a negative serum pregnancy test at screening and negative urine pregnancy test before the first application on Day 1 and must agree to take appropriate precautions to avoid pregnancy from screening through 30 days (1 menstrual cycle) after the last application of study ruxolitinib cream and must refrain from donating oocytes during this period. Permitted methods in preventing pregnancy (see Appendix A) should be communicated to the participants and their understanding confirmed.
 - c. Female participants not considered to be of childbearing potential as defined in Appendix A are eligible.

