10.1. Sample Size Determination

Approximately 180 participants will be randomized 1:1 to ruxolitinib 1.5% cream BID or vehicle cream BID.

The sample size is calculated to provide sufficient power (> 80%) to detect a difference between ruxolitinib 1.5% cream BID and vehicle cream BID for the primary and key secondary endpoints. The powers for different endpoints are provided in Table 9. The chi-square test with a 2-sided α of 0.05 is used to calculate the powers.

In addition to providing sufficient power for efficacy variables, the sample size is determined to provide an adequate database for safety evaluations.

Table 9: Powering for Primary and Key Secondary Endpoints

Variables	Response Rates With Ruxolitinib 1.5% Cream BID	Response Rates With Vehicle Cream BID	Power
IGA-CHE-TS at Week 16	26% ^{ab}	10% ^{abc}	80%
ITCH4 at Week 16	40% ^{bc}	18% ^{bc}	90%
ITCH4 at Week 4	35% ^{bc}	12% ^{bc}	95%
ITCH4 on Day 7	30% ^{bc}	10% ^{bc}	92%

^a Based on the results from a Phase 2b study of topical delgocitinib in CHE (Worm 2022).

^b Based on the results from a Phase 3 study of topical delgocitinib in CHE (Bissonnette 2023).

^c Based on the results from the 2 Phase 3 registrational AD studies, INCB 18424-303 and INCB 18424-304.

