10.4.2. Key Secondary Objective

If the primary objective is achieved, the statistical hypotheses for the key secondary endpoint will be tested in the order specified in Section 10.3. Key secondary efficacy analysis at Week 16, Week 4, and Week 1 (Day 7) will be conducted in the ITT population. The statistical comparisons for binary outcomes (ITCH4) will be analyzed using a similar method as specified in the primary analysis. The stratum-adjusted ITCH4 rate difference (1.5% BID vs vehicle) and 95% CI will be computed in a similar way as in the primary analysis. A summary of analyses for the key secondary endpoints is provided in Table 12.

Table 12: Summary of Analyses for Key Secondary Endpoints

Parameter	Definition
Treatment	Ruxolitinib 1.5% cream compared with vehicle cream
Population	ITT population
Variables	ITCH4 response at Week 16: Defined as a ≥ 4-point improvement in CHE-related Itch NRS score from baseline ITCH4 response at Week 4 ITCH4 response at Week 1 (Day 7)
Population-level summary	Stratum-adjusted IGA-CHE-TS rate difference with 95% CI

Note: Participants with missing observed data at the timepoint of interest, participants who discontinue study treatment at any time before the timepoint of interest, and participants who discontinue from the study for any reason will be defined as nonresponders. No rescue therapy or treatment switch is allowed in this study.

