## 3.3. Sample Size Considerations

Approximately 180 participants will be randomized 1:1 to ruxolitinib 1.5% cream BID or vehicle cream BID.

The sample size is calculated to provide sufficient power (> 80%) to detect a difference between ruxolitinib 1.5% cream BID and vehicle cream BID for the primary and key secondary endpoints. The powers for different endpoints are provided in Table 2. The chi-square test with a 2-sided  $\alpha$  of 0.05 is used to calculate the powers.

In addition to providing sufficient power for efficacy variables, the sample size is determined to provide an adequate database for safety evaluations.

**Table 2:** Powering for Primary and Key Secondary Endpoints

Variables	Response Rates With Ruxolitinib 1.5% Cream BID	Response Rates With Vehicle Cream BID	Power
IGA-CHE-TS at Week 16	26% a,b	10%a,b,c	80%
ITCH4 at Week 16	40%b,c	18%b,c	90%
ITCH4 at Week 4	35% b,c	12%b,c	95%
ITCH4 on Day 7	30%b,c	10%b,c	92%

<sup>a Based on the results from a Phase 2b study of topical delgocitinib in CHE (Worm et al 2022).

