#### 7.3.2. Primary Efficacy Analyses

The key parameters for the primary analysis are provided in Table 4. The primary analysis will be based on the ITT population in the DBVC period. The primary alternative hypothesis (superiority of active ruxolitinib 1.5% cream BID compared with vehicle) will be tested at a 2-sided  $\alpha = 0.05$  level using a CMH test stratified by stratification factors IGA-CHE score (3 or 4) and region (North America or outside of North America). The p-value and overall odds ratio

with 95% CI will be provided. Summary of IGA-CHE-TS rates will be reported for each treatment group. Stratum-adjusted IGA-CHE-TS rate difference (1.5% BID vs vehicle) and 95% CI will be computed using Mantel-Haenszel weights (Mantel and Haenszel 1959).

**Table 4:** Summary of Primary Analysis

Parameter	Definition	
Treatment	Ruxolitinib 1.5% cream compared with vehicle cream	
Population	ITT Population	
Variable	IGA-CHE-TS at Week 16: Defined as an IGA-CHE score of 0 or 1 with ≥ 2 grade improvement from baseline	
Population-level summary	Stratum-adjusted IGA-CHE-TS rate difference with 95% CI	

All nonresponders during the DBVC period, as well as all participants missing Week 16 assessment and who discontinue study treatment at any time before Week 16, or discontinue from the study for any reason, will be defined as nonresponders for the nonresponder imputation analysis.

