## 7.4.2. Key Secondary Efficacy Analysis

Key secondary efficacy analyses will be conducted in the ITT population in the DBVC period. If the primary objective is achieved, the statistical comparisons for key secondary endpoints will be tested with the procedures specified in Section 3.2. The same nonresponder imputation method as specified in the primary analysis will be used to handle missing Week 4 and Week 16 itch data.

For the key secondary endpoints of ITCH4 at Week 1 (Day 7), all participants who are missing Day 7 daily Itch NRS scores will be imputed using multiple imputation by fully conditional specification method. The variables to be included in the imputation regression model are treatment group, stratification factor, baseline itch score, and postbaseline daily itch score on Day 1 to Day 7. The corresponding binary response on Day 7 will be derived for each of the imputed datasets per the definition in Section 7.4.1.1.

The following sample SAS code will be used for the MI:

```
proc mi data=mi_wide seed=18424226 nimpute=30 out=impute_itch;
class trt01p strat1 strat2;
var trt01p strat1 strat2 base avald1 avald2 avald3 avald4 avald5
avald6 avald7;
fcs regpmm nbiter=30;
run;
```

All key secondary efficacy analyses will use stratified CMH test similar to the primary efficacy analysis. The summary of key secondary endpoints analysis is also provided in Table 5.

**Table 5:** Summary of Analyses for Key Secondary Endpoints

Parameter	Definition	
Treatment	Ruxolitinib 1.5% cream compared with vehicle cream	
Population	ITT population	
Variables	ITCH4 response at Week 16 ITCH4 response at Week 4 ITCH4 response at Week 1 (Day 7)	
Population-level summary	Stratum-adjusted IGA-CHE-TS rate difference with 95% CI	

Note 1: Participants with missing observed data at the timepoint of interest (Week 4, Week 16), participants who discontinue study treatment at any time before the timepoint of interest (Week 4, Week 16), and participants who discontinue from the study for any reason will be defined as nonresponders. Participants with missing observed data at Day 7 will be imputed using multiple imputation by fully conditional specification method. No rescue therapy or treatment switch is allowed in this study. Note 2: ITCH4 is defined as  $a \ge 4$ -point improvement in CHE-related Itch NRS score from baseline.

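### The three alpha-controlled ITCH4 tests are valid but leave out baseline itch; adjusting for it is a cheap gain in precision, nil to modest at Weeks 4 and 16 and more consistent at Day 7

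*SAP*

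**What the plan says.** SAP 3.2 places ITCH4 at Week 16, Week 4 and Day 7 after the primary endpoint in a fixed sequence at two-sided 0.05. SAP 7.4.2 gives the test: "All key secondary efficacy analyses will use stratified CMH test similar to the primary efficacy analysis". The primary analysis in SAP 7.3.2 is done "using a CMH test stratified by stratification factors IGA-CHE score (3 or 4) and region (North America or outside of North America". Protocol 10.4.2 agrees: "The statistical comparisons for binary outcomes (ITCH4) will be analyzed using a similar method as specified in the primary analysis". Baseline itch is neither a stratum nor a covariate in any of the three tests, and SAP 3.1 does not use it to stratify randomization.

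Baseline itch does appear in the Day 7 imputation: "The variables to be included in the imputation regression model are treatment group, stratification factor, baseline itch score", together with the daily scores from Day 1 to Day 7. Weeks 4 and 16 use nonresponder imputation, which has no model.

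Two baselines are in use. Protocol 5.1 requires "Baseline CHE-related Itch NRS score ≥ 4", taken as a 7-day mean with at least 4 days of data, and SAP 7.4.1.1 uses the 7-day mean for by-visit scores. For daily analyses, which I read as covering Day 7, SAP 7.4.1.1 takes the most recent single daily score in the week before Day 1.

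**The concern.** ITCH4 is a fixed 4-point fall on a 0 to 10 scale, so the follow-up score a participant must reach depends on where that participant started. Baseline itch is therefore a likely predictor of response. IGA-CHE and region were chosen for an investigator-rated endpoint and need not capture it.

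Leaving out a predictive covariate does not bias a randomized comparison. It does leave explainable variance in the rate difference, and a chance difference between arms in baseline itch passes into the estimate. At stake is some precision on three confirmatory endpoints, available from data already collected.

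**Working it through.** **1. Reproduce the stated power.** Inputs: "Approximately 180 participants will be randomized 1:1 to ruxolitinib 1.5% cream BID or vehicle cream BID" (90 per arm); "The chi-square test with a 2-sided α of 0.05 is used to calculate the powers"; rates from Protocol Table 9 and SAP Table 2.

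Power = Φ[(d − 1.96·SE0)/SE1], with SE0 = √(2p̄(1−p̄)/90) and SE1 = √([p1(1−p1)+p2(1−p2)]/90).

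| Endpoint | Rates | SE0 | SE1 | Power | Stated |
|---|---|---|---|---|---|
| Week 16 | 40% v 18% | 0.0676 | 0.0656 | 90.9% | 90% |
| Week 4 | 35% v 12% | 0.0632 | 0.0608 | 95.9% | 95% |
| Day 7 | 30% v 10% | 0.0596 | 0.0577 | 92.5% | 92% |

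The stated figures are met without any itch adjustment.

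**2. What baseline does to the threshold.** The follow-up score needed is baseline − 4.
- A baseline of 4 needs 0; a baseline of 10 needs 6.
- At Weeks 4 and 16 every eligible participant has a 7-day mean of at least 4, so response is always possible.
- At Day 7 a single-day baseline of 3 would need −1, so response is impossible. With an assumed day-to-day SD of 1.0 to 1.5, about 2% to 5% of participants would start below 4.

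**3. Size of the precision gain (assumed inputs).** VR is the unadjusted variance of the rate difference divided by the adjusted variance.

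*Week 16.* 180 participants, 40% v 18%, baseline itch truncated-normal on 4–10 with mean 7 and SD 1.7, residual SD 2.2, 5% nonresponder imputation, 4,000 trials per setting:

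| Slope of follow-up on baseline | 0.2 | 0.4 | 0.6 | 0.8 | 1.0 |
|---|---|---|---|---|---|
| VR | 1.12 | 1.06 | 1.01 | 0.98 | 0.98 |

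A separate simulation over slopes 0.2 to 1.0 gave 1.12 to 1.00. At slope 1.0 change does not depend on baseline and nothing is gained. Other assumed settings gave 1.01–1.08 and, with no missing data, 1.01–1.14.

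*Day 7, single-day baseline.* VR was about 1.05–1.16. Other settings gave 1.06–1.19, and one set had SE ratios of 0.975 to 0.900, which is 1/0.975² = 1.05 to 1/0.900² = 1.23.

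**4. Turn VR into power.** Divide both SEs by √VR.
- Week 16, VR 1.12: (0.22×1.0583 − 0.1326)/0.0656 = 1.53, power 93.7%; gain 93.7 − 90.9 = 2.8 points. At VR 1.00 the gain is 0.
- Day 7, VR 1.05: (0.20×1.0247 − 0.1169)/0.0577 = 1.53, power 93.6%; gain 1.1 points.
- Day 7, VR 1.16: (0.20×1.0770 − 0.1169)/0.0577 = 1.71, power 95.6%; gain 3.1 points.

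Simulation with a size-controlled SE gave about 1.5 to 3 points at Day 7. Runs whose SE had only a degrees-of-freedom correction showed up to about 5 points, which I do not rely on because of step 5.

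For the weekly-mean endpoints, a further simulation (mean 6.8, SD 1.6, 3,000 trials) separated the effect of itch from the change of test. Adding itch to a standardized model moved Week 16 power from 90.3% to 91.5%, 90.5% to 91.3% and 91.9% to 91.8% under three assumed links. Week 4 moved by 0.7, 0.4 and 0.0 points. Adding itch tertiles to the CMH strata instead gave essentially no gain (Week 16: 89.6% to 89.2%).

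**5. Type I error.** In 8,000 null trials per setting (Monte Carlo SE √(0.05×0.95/8000) = 0.24 points), the uncorrected influence-function SE gave 5.3% to 6.0% at null rates of 10%, 12% and 18%. CMH gave 4.6% to 5.1%. A leverage-corrected (HC3-type) SE gave 4.8% to 5.2%.

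**6. Chance imbalance.** In simulation, each 1-point difference between arms in mean baseline itch moved the unadjusted rate difference by 4 to 11 percentage points at Week 16 and 6 to 8 at Day 7. The adjusted estimate moved by about 1 or less. A 2-SD imbalance at Day 7 is about 0.5 to 0.6 points, so the shift is 0.5×6 = 3 to 0.6×8 ≈ 5 percentage points against a planned difference of 20. This is the same variance as in step 3 seen within one trial, not a second gain.

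**The case against.** The strongest case for leaving the plan alone is this. CMH on the randomization factors is a sound test, and Protocol and SAP agree on it. Power is already 91% to 96% by calculation. Every figure for the gain rests on an itch distribution and a slope that the documents do not give, and the gain disappears when change is unrelated to baseline. The change replaces a test that holds its size with one that does so only if the SE is computed carefully. The opening of Protocol Section 10 also allows that a change in methods for these hypotheses may lead to a Protocol amendment, so the cost may exceed a few lines of code.

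Most of this stands, and it is why the point is an improvement and not an error. It does not remove the point. With the leverage correction, size is held and Day 7 power still rises.

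Three stronger readings are tempting but unsupported:
- That the planned tests are wrong or biased. They are not; CMH kept its size in every null setting.
- That low baseline itch bars some participants from response at all three timepoints. The entry floor rules that out at Weeks 4 and 16; it can happen only with the Day 7 single-day baseline.
- That the SAP already relies on baseline itch to handle missing data at all three timepoints. It does so for Day 7 only.

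**Conclusion.** A cheap improvement to a valid analysis. At Week 16 the variance ratio is about 1.0 to 1.12 and the power gain about 0 to 3 points; at Week 4 the simulated gain was under 1 point; at Day 7 the ratio is about 1.05 to 1.16 and the gain about 1.5 to 3 points. Adjustment also largely removes the effect of a chance imbalance in baseline itch on the estimate. All these figures depend on assumed itch distributions, slopes and day-to-day variation. The case is firmest at Day 7, where the noisier single-day baseline enters the change score directly and can make response impossible. At Weeks 4 and 16 the gain may be near nil.

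**What to change.** In SAP 7.4.2, before the primary database lock:
- For each ITCH4 endpoint, prespecify a logistic model with treatment, IGA-CHE, region and the continuous baseline itch defined for that endpoint: the 7-day mean for Weeks 4 and 16, the last daily score for Day 7.
- Report the standardized (marginal) rate difference with 95% CI and p-value, using a small-sample, leverage-corrected (HC3-type) robust SE. Name the correction in the text; calling the SE robust is not enough.
- For Day 7, combine the standardized differences and their variances over the 30 imputations by Rubin's rules.
- Keep the stratified CMH result as supportive.
- Record the departure from the method in Protocol 10.4.2 in SAP 11.1, which now lists no changes, and decide whether the opening of Protocol Section 10 calls for an amendment.

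If only one endpoint is changed, it should be Day 7. No new data are needed and the summary measure remains a stratum- and covariate-adjusted rate difference. The costs are SAP wording and code, a key-secondary test that differs from the primary test, dependence on the SE correction to hold size, and possibly little return at Weeks 4 and 16.

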## 7.5. Analysis of Secondary Efficacy Parameters

## 7.5.1. Secondary Efficacy Measure

## 7.5.1.1. Hand Eczema Severity Index Score

The HECSI divides the hand into 5 areas for assessment (fingertips, fingers [except the tips], palms, back of hands, and wrists). Each of the 5 areas of the hand are assessed separately for erythema, induration/papulation, vesicles, fissuring, scaling, and edema using the following scale: 0, no skin changes; 1, mild disease; 2, moderate disease; and 3, severe disease. To determine the HECSI score, the affected area for each location (total of both hands) is given a score from 0 to 4 (0, 0%; 1, 1%-25%; 2, 26%-50%; 3, 51%-75%; and 4, 76%-100%) based on the extent of clinical symptoms. Finally, the score given for the extent at each location is multiplied by the total sum of the intensity of each clinical feature to calculate the total HECSI score, varying from 0 to a maximum severity score of 360 points (Held et al 2005).

The binary variable HECSI-75 will be equal to 1 for percentage improvement from baseline in HECSI-75 of  $\geq$  75% and will be equal to 0 for percentage improvement of < 75%. Hand Eczema Severity Index-90 is defined with the same pattern.

#### 7.5.1.2. Chronic Hand Eczema-Related Skin Pain Numerical Rating Scale Score

The CHE-related Skin Pain NRS is a once-per-24 hours ("daily") patient-reported measure of the worst skin pain severity of their CHE assessed using an 11-point scale (0 = no pain to 10 = worst imaginable pain), in the evening beginning on the day of screening through Week 32 or ET.

The CHE-related Skin Pain NRS score for baseline will be determined by averaging the 7 daily NRS scores before Day 1 (Day –7 to Day –1). The by-visit CHE-related Skin Pain NRS score for postbaseline visits will be determined by averaging the 7 daily NRS scores before the visit day. If 4 or more daily scores are missing (out of the 7), the CHE-related Skin Pain NRS score at the visit will be set to missing. For all the daily pain-related analyses, baseline will be defined as the last available pain NRS score during the last week prior to Day 1 (from Day –7 to Day –1).

The proportion of participants with a clinically relevant change in CHE-related Skin Pain, defined as a  $\geq$  2-point improvement in CHE-related skin pain NRS score from baseline to Week 16, will be summarized by treatment groups.

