#### 7.5.2. Secondary Efficacy Analysis

All secondary efficacy analyses will be conducted based on the ITT population during the treatment period (DBVC and OLE periods).

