## 7.5.2.3. Time-To-Event Efficacy Endpoints

For the time to achieve CHE-related Itch NRS score improvement of at least 4 points and time to achieve CHE-related Skin Pain NRS score improvement of at least 2 points, a log-rank test stratified by randomization stratification factors will be used for between treatment group comparisons. The hazard ratio and its 95% CI will be estimated based on the stratified Cox regression model using Efron's method accounting for ties. Kaplan-Meier curves will be presented by treatment groups. The number of participants, number of events and number of

censoring will be summarized by treatment groups. The Kaplan-Meier estimate of median time will be presented with its 95% CI. The 95% CI will be calculated using the method by Brookmeyer and Crowley (1982).

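### The ≥ 2-point skin-pain response analyses include ITT participants whose baseline pain is below 2 and who cannot respond, which dilutes a nominal secondary comparison by an unknown amount

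*SAP*

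**What the plan says.** SAP 7.5.1.2 scores skin pain daily from 0 to 10 and defines a clinically relevant change as at least a "2-point improvement in CHE-related skin pain NRS score from baseline to Week 16". It attaches no minimum starting score.

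The same section gives two baselines. For by-visit scores, "The CHE-related Skin Pain NRS score for baseline will be determined by averaging the 7 daily NRS scores before Day 1". For daily pain analyses, "baseline will be defined as the last available pain NRS score during the last week prior to Day 1". It does not say which one the time-to-response analysis uses. The parallel itch text in SAP 7.4.1.1 does: it assigns time-to-improvement to the daily baseline.

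The only symptom score required at entry is itch: "Baseline CHE-related Itch NRS score ≥ 4" (Protocol 5.1). Neither the inclusion nor the exclusion criteria mention a skin-pain score.

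On the analysis set, SAP 7.5.2 states: "All secondary efficacy analyses will be conducted based on the ITT population". SAP 5.3.1 defines ITT as everyone randomised. In SAP Appendix A, Tables 2.3.1 and 2.3.3 and Figures 4.4.1 and 4.4.3 (pain response and time to pain response) are all listed as ITT.

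The two endpoints are handled differently. SAP 7.5.2.2 only summarises the Week 16 proportion. SAP 7.5.2.3 specifies a test: for "time to achieve CHE-related Skin Pain NRS score improvement of at least 2 points, a log-rank test stratified by randomization stratification factors will be used" to compare the groups, with a stratified Cox hazard ratio, Kaplan-Meier curves and a median with its 95% CI. Neither endpoint is in the fixed testing sequence of SAP 3.2.

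**The concern.** A responder definition needs room on the scale for the response. For itch the plan provides it: the entry minimum of 4, on the 7-day mean, equals the 4-point ITCH4 threshold, so every eligible participant can respond on that baseline. For pain nothing plays this part. Participants with little or no pain at entry are carried through the pain analyses as if treatment had failed them.

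At stake is the reading of one secondary comparison. The observed difference in proportions would partly reflect how many participants had pain at entry. The hazard ratio would move towards 1, the Kaplan-Meier curves would level off lower, and the log-rank test would lose power to people who carry no information about response.

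**Working it through.** **Inputs from the documents.** 180 participants randomised 1:1, so 90 per arm; two-sided α = 0.05 (Protocol 10.1, SAP 3.3). Scale 0-10 and threshold 2 (SAP 7.5.1.2). No pain minimum at entry (Protocol 5.1). Analysis set ITT (SAP 5.3.1, 7.5.2).

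**Inputs not in the documents, so assumed.** The share f of each arm with baseline pain below 2 (range 0-30%), and response rates by Week 16 among those able to respond (60% vs 40%). Randomisation makes f equal between arms in expectation.

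**1. The plan's own figures.** The documents state no power for pain. The powers they do state reproduce with the chi-square formula

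power = Φ{ [|p1 − p2| − 1.96·√(2p̄(1 − p̄)/n)] / √([p1(1 − p1) + p2(1 − p2)]/n) }.

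For IGA-CHE-TS, 26% vs 10%, n = 90, p̄ = 0.18: (0.16 − 1.96 × 0.0573)/0.0560 = 0.85, so power is 80.3% (stated 80%). The ITCH4 endpoints give 90.9%, 95.9% and 92.5% (stated 90%, 95%, 92%). This confirms 90 per arm as the basis.

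**2. The floor.** The lowest score is 0, so the largest possible improvement equals the baseline score B. If B < 2, an improvement of 2 is impossible.

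**3. Dilution.** ITT rate = (1 − f) × rate among those able to respond, in each arm, so the ITT difference = (1 − f) × 20 points.

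**4. Log-rank power.** Simulated trials with 90 per arm, exponential times giving 60% vs 40% events by Day 112 (hazard ratio ln 0.4/ln 0.6 = 1.79), censoring at Day 112, a fraction f that never has an event, and an unstratified two-sided test.

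| f | ITT rates | ITT difference | Power, ITT | Power, baseline ≥ 2 only |
|---|---|---|---|---|
| 0% | 60% vs 40% | 20 points | 78% | 78% |
| 5% | 57% vs 38% | 19 points | 76% | 78% |
| 10% | 54% vs 36% | 18 points | 72% | 74% |
| 20% | 48% vs 32% | 16 points | 60% | 67% |
| 30% | 42% vs 28% | 14 points | 51% | 62% |

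Separate simulation runs agree to within about 2 points, so gaps of 2 points are at the level of simulation error.

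**5. Kaplan-Meier median.** The active arm's median is no longer reached by Week 16 once 0.60 × (1 − f) < 0.50, that is, f > 1/6, or about 17%.

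**6. Other assumed rates.** With a true hazard ratio of 1.7, at f = 10, 20 and 30%:
- 60% vehicle response among those able to respond: ITT hazard ratio 1.63, 1.56, 1.51; power 74, 60, 48% in ITT against 81, 75, 69% restricted.
- 40% vehicle response: ITT hazard ratio 1.66, 1.62, 1.62; power 60, 51, 46% in ITT against 64, 60, 56% restricted.

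The power loss against the restricted set is therefore 4 to 21 points over this range. Restricting gains power despite the smaller denominator because those removed cannot have an event in either arm.

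**The case against.** **The size is unknown and may be small.** Entry requires IGA-CHE 3 or 4. In SAP Table 3, grade 3 requires at least one moderate sign among vesiculation, edema and fissures. Protocol 2.1.1 lists pain as a typical symptom, and the diary item asks for the worst pain in 24 hours. All this makes a low f plausible. It does not establish one, so the point stands with its size left open.

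**The stakes are limited.** This stands. The Week 16 proportion is descriptive, so no power argument applies to it. The log-rank p-value is nominal, and the trial was not sized on pain.

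**The plan already gives some protection.** By-visit change in Skin Pain NRS has no 2-point threshold (SAP 7.5.2.1), and baseline pain is summarised (SAP 6.1.2). A reader could therefore suspect a floor effect, but could not recover the hazard ratio or proportion among those able to respond.

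**ITT answers a legitimate question:** what share of all randomised participants gain 2 points. This is fair, and is why the ITT result should stay in view.

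**A stronger reading about the baseline.** A reader might infer that a single daily score as baseline puts more people below 2 than the 7-day mean. The documents do not support this. On one integer score, below 2 means 0 or 1; on a mean, 1.1 to 1.9 also falls below 2. Under assumed score distributions the direction changes: 25% for the single score against 30% for the mean in one setting (underlying mean 3, between- and within-person SDs 2 and 1), but 11.5% against 11.1% in another with a higher mean and larger SDs. The SAP also leaves open which baseline the time-to-response analysis uses.

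**Conclusion.** The point holds as a matter of arithmetic and text: both pain-response analyses include participants who cannot respond, and nothing at entry or in the analysis set prevents it. The consequence is attenuation by (1 − f) and lost power in one nominal secondary comparison. Under the assumed 60% vs 40% it ranges from negligible at f near 0-5% to a 6-point smaller difference and about 11 points less power than the restricted set at f = 30%. Those sizes rest wholly on assumed f and response rates.

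A reader might go further and infer that a confirmatory result is at risk or that the pain comparison is biased in favour of treatment. Neither follows. The pain endpoints lie outside the fixed sequence, low-pain participants are balanced between arms in expectation, type I error is not inflated, and the primary and key secondary endpoints are untouched.

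**What to change.** Amend SAP 7.5.1.2, 7.5.2.2 and 7.5.2.3 before unblinding, so that the restriction cannot look data-driven:

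- Prespecify the ≥ 2-point skin-pain proportion and the time-to-response analysis in ITT participants with baseline Skin Pain NRS ≥ 2.
- State whether the time-to-response analysis uses the 7-day mean or the last daily score, and define each analysis's subset on the baseline that analysis uses.
- Report the number excluded per arm.
- Present the full-ITT result alongside, and update the Appendix A entries to match.
- Describe the pain log-rank p-value as nominal.

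The cost is SAP wording, a baseline flag and a few extra displays. The subset is fixed before treatment, so the randomised comparison is preserved. The downsides are a smaller denominator and a target population limited to participants with pain at entry, which is a reason to show both results. This is a cheap improvement; if f proves to be near zero, the two analyses will nearly coincide.
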